5.4 PARTICIPANT WITHDRAWAL OR TERMINATION

5.4.1 REASONS FOR WITHDRAWAL OR TERMINATION

Participants are free to withdraw from participation in the study at any time upon request. The study investigator or the funding source of the study ("Regeneron") can remove participants from the study without their consent at any time for any reason including:

- If any treatment-related Grade 4 adverse events (AE) develops during Cemiplimab-rwlc therapy.
- If any clinically adverse event (AE), laboratory abnormality, or other medical condition or situation occurs such that continued participation in the study would not be in the best interests of the participant.

- If the participant meets any exclusion criteria (either newly developed or not previously recognized) that precludes further study participation.
- Extraordinary medical circumstances: If at any time the constraints of this protocol are detrimental to the patient's health, the protocol treatment should be discontinued.
- If patient develops progressive disease, then the patient will discontinue the protocol therapy.
- If patient develops unacceptable toxicity, then the patient will discontinue the protocol therapy.

The reason and date for patient removal from the study must be documented in the Case Report Form (CRF).

The same procedures will be followed as those that would happen if participants decided to discontinue from the study.

5.4.2 HANDLING OF PARTICIPANT WITHDRAWALS OR TERMINATION

Every effort will be made to undertake protocol-specified safety follow-up procedures to capture AEs, serious adverse events (SAEs), and unanticipated problems.

Those who discontinue protocol therapy early will be followed for response until progression and for survival for 1 year from the date of withdraw or termination.

Patients removed from study for unacceptable adverse events will be followed until resolution or stabilization of the adverse event.

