Exploratory Objective:

1. Identify potential biomarkers related to response to Cemiplimab-rwlc in immunocompromised patients with unresectable locally recurrent and/or metastatic CSCC.
2. Evaluate overall response rate of underlying chronic lymphocytic leukemia (CLL) in the CLL subset.

Primary Endpoint: Overall response rate of CSCC

Secondary Endpoint:

1. Progression-free survival
2. Overall survival
3. Acute and late immune-related and non-immune-related toxicities

Exploratory Endpoint:

1. Predictive biomarkers of Cemiplimab-rwlc response in CSCC
2. Overall response rate of underlying CLL in the CLL subset

Population: Immunocompromised patients with unresectable locally recurrent and/or metastatic CSCC.

Sample size: 27 patients.

Study groups: immunocompromised patients with unresectable locally recurrent and/or metastatic CSCC

Phase: Phase II

[figure not shown]
Number of Sites enrolling participants: 6

Description of Study Agent: Cemiplimab-rwlc

Study Duration: 24 months

Treatment Duration: 12 months

SCHEMA OF STUDY DESIGN

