7.3.5 FOLLOW-UP

To assess for late toxicities, at 6 months and 12 months after EOT patients will return for a physical exam and labs, unless the patient has enrolled in hospice care or is otherwise unwilling/unable to return to clinic.

For this protocol, all patients, including those who discontinue protocol therapy early, will be followed for response until progression and for survival for 2 years from the start of treatment. All patients must also be followed through completion of all protocol therapy. Patients removed from study for unacceptable adverse events will be followed until resolution or stabilization of the adverse event. Follow-up for survival will be performed every 90 days (\pm 2 weeks) from the end of treatment visit.

Research blood collection to be performed at the end of study (2 years after initiation of study treatment).

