i: All concomitant prescription medications taken during study participation will be recorded on the case report forms (CRFs).

j: AEs/SAEs will be assessed during each visit clinically and based on laboratory data. Patients will be encouraged to report AEs/SAEs at the earliest recognition via the phone between the visits.

k: End of Treatment visit is to occur 30 days after the last dose of Cemiplimab-rwlc therapy ± 7 days. If the subject is unable or unwilling to return to clinic this visit can be conducted via a telephone call.

l: May be omitted if performed within the last 8 weeks.

m: Physical exam and labs required at 6 months and 12 months after EOT only to assess for late AEs, unless the patient has enrolled in hospice care or is otherwise unwilling/unable to return to clinic.

n: Research blood collection to be performed at the end of study (2 years after initiation of study treatment).

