10.4.2 ANALYSIS OF THE PRIMARY EFFICACY ENDPOINT(S)

The primary endpoint for efficacy analyses is the ORR. All response assessments are done by RECIST 1.1 analysis of radiologic scans. In some patients, response assessments include photos and radiologic scans and evaluated by composite efficacy criteria (see Appendix 2). Clinical lesions will only be considered measurable when they are superficial (eg, skin nodules and palpable lymph nodes) and ≥ 10 mm (≥ 1 cm) diameter as assessed using calipers (e.g., skin nodules). In the case of skin lesions, documentation by color photography, including a ruler to estimate the size of the lesion, is recommended. Patients who are deemed as not evaluable according to RECIST 1.1 or inevaluable by the composite efficacy criteria will be considered as not reaching PR/CR for ORR.

We expect to complete the accrual in 12 months and the total study duration will be 24 months.

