10.4.3 ANALYSIS OF THE SECONDARY ENDPOINT(S)

The secondary analyses of efficacy as measured by PFS and OS will be summarized by median and its 95% confidence interval using the Kaplan-Meier method.

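### Sections 5.4.2 and 7.3.5 set different survival follow-up for patients who stop treatment early, and the 24-month total duration in 10.4.2 is about 12 months too short for the 7.3.5 schedule

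*Combined protocol and SAP*

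**What the plan says.** **Survival follow-up.** Section 5.4.2 says that patients who "discontinue protocol therapy early will be followed for response until progression and for survival for 1 year from the date of withdraw or termination". It does not say whether that date is when treatment stops or when the patient leaves the study. Section 7.3.5 says that "all patients, including those who discontinue protocol therapy early, will be followed for response until progression and for survival for 2 years from the start" (meaning the first dose). Section 5.4.1 adds: "If patient develops progressive disease, then the patient will discontinue the protocol therapy".

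**Duration.** Section 10.4.2 states: "We expect to complete the accrual in 12 months and the total study duration will be 24 months". The Study Summary has "Study Duration: 24 months", without saying whether this is per patient or for the whole study. Table 3 note m reads "Physical exam and labs required at 6 months and 12 months after EOT only to assess for late AEs", and note n reads "Research blood collection to be performed at the end of study (2 years after initiation of study treatment".

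**Analysis.** Under section 10.4.3, "PFS and OS will be summarized by median and its 95% confidence interval using the Kaplan-Meier method". Section 10 gives neither a censoring rule nor a data cut-off for OS.

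**The concern.** Sections 5.4.2 and 7.3.5 name the same group, so they cannot be read as covering different patients. A patient who progresses on treatment must stop under 5.4.1 and then falls under both rules.

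If a site applied 5.4.2, the end of OS follow-up would depend on when treatment stopped, and stopping is linked to prognosis. Kaplan-Meier assumes that censored patients have the same later risk as those still followed. That assumption would be doubtful here, and the OS estimate could be biased. The Study Summary lists six enrolling sites, so different sites could also censor similar patients differently.

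The duration conflict matters differently. If the study closed 24 calendar months after it opened, the last patient entered would have 12 months of survival follow-up and would miss the 2-year blood sample. If that patient completed treatment, the 12-month late-toxicity visit would also be missed. This would be administrative censoring by entry date. It loses information but does not by itself bias Kaplan-Meier.

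**Working it through.** **1. Gap between the two survival rules.** Let s be the month of stopping treatment, and read the 5.4.2 date as that date. Follow-up ends at s + 12 under 5.4.2 and at 24 under 7.3.5, so the shortfall is 24 − (s + 12) = 12 − s.

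| Stop at month | End under 5.4.2 | End under 7.3.5 | Shortfall (months) |
|---|---|---|---|
| 3 | 15 | 24 | 9 |
| 6 | 18 | 24 | 6 |
| 9 | 21 | 24 | 3 |

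The rules agree only at s = 12, which is full treatment. If the 5.4.2 date means leaving the study, the shortfall is 12 minus the month of leaving, and there is none from month 12 on.

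**2. Duration.** Inputs: accrual 12 months and total 24 months (10.4.2); survival follow-up 24 months from treatment start (7.3.5); 17 cycles of 21 days (6.1.9, Table 3); end-of-treatment (EOT) visit 30 days after the last dose (7.3.4); last late-toxicity visit 12 months after EOT (7.3.5).

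- The stated 24 months can be reproduced in two ways only: 12 accrual + 12 treatment with no follow-up, or one patient's 24 months.
- From survival follow-up: 12 + 24 = 36 months.
- From the late-toxicity visits: the last dose is 16 × 21 = 336 days after the first. EOT is at 336 + 30 = 366 days, or 366 / 30.44 = 12.02 months. The last visit is at 24.02 months. For a patient entered at month 12, that is about month 36.

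Both routes give about 36 months against the stated 24.

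**3. What applying 5.4.2 could do to OS.** The documents give no hazards or stopping rates, so these are assumptions for illustration. A share f belongs to the early-stopping group with constant monthly hazard h1, and the rest have h2.

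- True survival: S(t) = f·e^(−h1·t) + (1 − f)·e^(−h2·t).
- With early stoppers censored at c = s + 12, the Kaplan-Meier estimate tends to S(c)·e^(−h2·(24 − c)) at month 24.

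Example: f = 0.5, h1 = 0.06, h2 = 0.02, s = 3. S(24) = 0.428 and S(15) = 0.574, so the estimate is 0.574 × e^(−0.18) = 0.479, which is 5.1 points too high.

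| f | h1 / h2 | True 24-month OS | Bias, stop at 3 / 6 / 9 (points) | True median (months) | Median under 5.4.2 (months) |
|---|---|---|---|---|---|
| 0.5 | 0.06 / 0.02 | 42.8% | +5.1 / +3.2 / +1.5 | 19.1 | 21.9 / 19.8 / 19.1 |
| 0.25 | 0.06 / 0.02 | 52.3% | +2.6 / +1.6 / +0.8 | not reached by 24 | not reached by 24 |
| 0.5 | 0.02 / 0.06 | 42.8% | −9.4 / −6.6 / −3.5 | 19.1 | 17.3 / 18.6 / 19.1 |
| 0.25 | 0.02 / 0.06 | 33.2% | −4.7 / −3.3 / −1.7 | 14.6 | 14.6 for all three |

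With equal hazards the bias is zero. The median does not move if it falls before the 5.4.2 censoring starts.

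Deaths between the 5.4.2 cut-off and month 24 that would go unrecorded (first row of the table): 27 × 0.5 × (e^(−0.06c) − e^(−1.44)) = 2.3 / 1.4 / 0.6 for stops at month 3 / 6 / 9.

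**The case against.** **The 24 months may not be an error.** The sentence sits in the primary-endpoint section, and 12 months of accrual plus 12 of treatment is exactly 24, the time needed to finish on-treatment response assessment in the last patient. The Study Summary figure also fits a per-patient reading. The arithmetic is right, but 10.4.2 refers to the total duration of the study directly after accrual, and 7.3.5 places end of study 2 years after treatment start. The accrual-plus-treatment reading leaves out follow-up that the protocol requires. The per-patient reading is reasonable for the Study Summary line only.

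**The OS figures rest on invented hazards.** This stands as a limit on what they show. Even the sign is undetermined, and the largest value comes from the case where early stoppers die more slowly, which is the less plausible one if stopping follows progression. The model also applies 0.06 from month 0, so with f = 0.5 only about 42% / 35% / 29% of all patients are alive in the stopping group at month 3 / 6 / 9. If 0.06 applies only after stopping and 0.02 before, the overstatement is 5.8 / 4.1 / 2.2 points. The conclusion does not change.

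**The effect is small beside the sampling error.** With 27 patients, the standard error of a 42.8% survival proportion is √(0.428 × 0.572 / 27) = 9.5 points, and the planned summary is the median, which often does not move. This is fair, and it is a reason to rate the point as moderate. It does not remove the conflict between the two sections.

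**Conclusion.** Both conflicts are real and stand in the current text. Sections 5.4.2 and 7.3.5 give the same patients different survival follow-up, with a shortfall of 12 − s months if the 5.4.2 date is the date of stopping treatment. The total duration in 10.4.2 is about 12 months shorter than the 7.3.5 schedule needs with 12 months of accrual.

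The consequence is confined to OS and late-toxicity follow-up. Any OS bias arises only if 5.4.2 is applied, and its size and direction rest on assumed hazards and stopping rates. If 7.3.5 is applied to everyone, there is no such bias and both points are conflicts of wording. Follow-up for response runs to progression in both sections. The response-rate test, its alpha and its power are unaffected. The plan should be corrected, but the primary analysis is not at risk.

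**What to change.** - Put one survival follow-up rule in 5.4.2 and 7.3.5. The 7.3.5 rule avoids censoring that depends on stopping treatment and matches Table 3 note n. The sponsor should confirm that it is the intended rule.
- Restate the total duration in 10.4.2 as about 36 months (12 accrual + 24 follow-up).
- Label the Study Summary's 24 months as per patient.
- State that the data cut-off for OS and late toxicity is the end of that follow-up.

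The cost is amendment wording only, because 7.3.5 already requires this follow-up. The drawback is that the stated study end and the final report move about 12 months later.

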5.5 PREMATURE TERMINATION OR SUSPENSION OF STUDY

This study may be temporarily suspended or prematurely terminated by the investigators. Circumstances that may warrant termination or suspension include, but are not limited to:

- Determination of unexpected, significant, or unacceptable risk to participants.
- Demonstration of efficacy that would warrant stopping.
- Insufficient compliance to protocol requirements.
- Data that is not sufficiently complete and/or evaluable.
- Determination of futility.

If the study is prematurely terminated or suspended, the PI will promptly inform the IRB and will provide the reason for the termination or suspension.

Study may resume once concerns about safety, protocol compliance, data quality are addressed and satisfy the PI and IRB.

6 STUDY AGENT

6.1 STUDY AGENT(S) AND CONTROL DESCRIPTION

6.1.1 ACQUISITION

Cemiplimab-rwlc will be supplied by Regeneron Pharmaceuticals, Inc. Cemiplimab-rwlc will be shipped at a temperature of 2° to 8°C to the investigator or designee at regular intervals or as needed during the study. At specified time points during the study (eg, interim site monitoring visits), at the site close-out visit, and following drug reconciliation and documentation by the site monitor, all opened and unopened study drug will be destroyed or returned to Regeneron Pharmaceuticals, Inc. or designee.

6.1.2 FORMULATION, APPEARANCE, PACKAGING, AND LABELING

Cemiplimab-rwlc will be supplied as a liquid in sterile, single-use vials. Each vial will contain Cemiplimab at a concentration of 25 mg/mL or 50 mg/mL.

6.1.3 PRODUCT STORAGE AND STABILITY

Cemiplimab-rwlc will be refrigerated at the site at a temperature of 2° to 8°C, and refrigerator temperature will be logged daily. Further storage instructions will be provided in the pharmacy manual.

6.1.4 PREPARATION

Visually inspect for particulate matter and discoloration prior to administration. Cemiplimab-rwlc is a clear to slightly opalescent, colorless to pale yellow solution that may contain trace amounts of translucent to white particles. Discard the vial if the solution is cloudy, discolored or contains extraneous particulate matter other than trace amounts of translucent to white particles.

Preparation:

- Do not shake.
- Withdraw 7 mL from a vial and dilute with 0.9% Sodium Chloride Injection, USP or 5% Dextrose Injection, USP to a final concentration between 1 mg/mL to 20 mg/mL.
- Mix diluted solution by gentle inversion. Do not shake.
- Discard any unused medicinal product or waste material.

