4 STUDY DESIGN AND ENDPOINTS

4.1 DESCRIPTION OF THE STUDY DESIGN

This is a single arm phase II study to evaluate the efficacy of Cemiplimab-rwlc in immunocompromised patients with unresectable locally recurrent or metastatic CSCC.

Eligible patients will be given Cemiplimab-rwlc 350 mg IV every 3 weeks. This will be administered until patients get severe side effects, disease progression, or for a period of 1 year (whichever point is reached first).

A scan will be performed approximately every 9 weeks till the time that the patient is receiving the treatment. We plan to recruit 27 patients.

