6.1.5 DOSING AND ADMINISTRATION

A pharmacist or other qualified individual will be identified at each site to prepare Cemiplimab-rwlc for administration. The planned dose and schedule of Cemiplimab-rwlc is 350 mg IV over approximately 30 minutes every 21 days (+/- 3 days).

Storage of Infusion Solution:

- Store at room temperature up to 25 °C (77 °F) for no more than 8 hours from the time of preparation to the end of the infusion or at 2 °C to 8 °C (36 °F to 46 °F) for no more than 24 hours from the time of preparation to the end of infusion.
- Allow the diluted solution to come to room temperature prior to administration.
- Do not freeze.

Administration:

- Administer by intravenous infusion over 30 minutes through an intravenous line containing a sterile, in-line or add-on 0.2 micron to 5-micron filter.

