6.1.7 STARTING DOSE AND DOSE ESCALATION SCHEDULE

Cemiplimab-rwlc is administered as a flat dose of 350 mg IV over approximately 30 minutes every 21 days (+/- 3 days).

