- Patients with grade ≥ 2 uveitis. Patients with grade 2 uveitis will generally be discontinued from study treatment, unless there is resolution to grade ≤ 1 AND discussion with and approval by the site principal investigators. All patients with grade ≥ 3 uveitis will be permanently discontinued from study treatment.

After other AEs, resumption of treatment may be at the initial dose level. A patient who does not

tolerate Cemiplimab-rwlc will be removed from the study. Refer to [Appendix 1](#) for additional management guidelines for immune-related toxicities.

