6.1.9 DURATION OF THERAPY

Patients will be treated for 1 year (17 cycles) unless they have disease progression, intolerable toxicities or withdraw consents.

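### Section 6.1.4 gives one 7 mL withdrawal volume for two permitted vial strengths; it delivers 350 mg only at 50 mg/mL and half the dose, 175 mg, at 25 mg/mL

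*Combined protocol and SAP*

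**What the plan says.** Section 6.1.2 describes the supplied product: "Each vial will contain Cemiplimab at a concentration of 25 mg/mL or 50 mg/mL". Section 6.1.4 then tells the preparer: "Withdraw 7 mL from a vial and dilute with 0.9% Sodium Chloride Injection" (5% dextrose is the alternative diluent), "to a final concentration between 1 mg/mL to 20 mg/mL". The 7 mL carries no condition on strength.

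The dose is fixed in milligrams in three places:

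- Section 4.1: "Eligible patients will be given Cemiplimab-rwlc 350 mg IV every 3 weeks".
- Section 6.1.5: "The planned dose and schedule of Cemiplimab-rwlc is 350 mg IV over approximately 30 minutes".
- Section 6.1.7: "Cemiplimab-rwlc is administered as a flat dose of 350 mg IV over approximately 30 minutes".

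Section 6.1.8 rules out dose reduction. Section 6.1.3 mentions a pharmacy manual, but only for storage.

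On a separate, minor point, section 6.1.8 says of all patients at grade 3 or above that "uveitis will be permanently discontinued from study treatment". The Grade 3-4 uveitis row of Appendix 1 also says to discontinue, but closes with a line on obtaining site PI approval before treatment resumes.

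**The concern.** A fixed volume gives a fixed dose only if the concentration is fixed, and section 6.1.2 permits two concentrations that differ by a factor of two. Anyone who follows section 6.1.4 to the letter with a 25 mg/mL vial prepares half the protocol dose, in a protocol that permits no reduction.

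Patients with unresectable or metastatic disease would be under-treated. If the error went unnoticed, patients at two exposures would also be pooled in one response rate from 27 patients, with no control arm against which the difference might show.

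The uveitis text raises a smaller worry of the same kind: two parts of the protocol point different ways on whether treatment can restart after a Grade 3-4 event.

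**Working it through.** **Inputs.** Dose 350 mg (sections 4.1, 6.1.5, 6.1.7). Vial strengths 25 and 50 mg/mL (6.1.2). Volume withdrawn 7 mL and final concentration 1 to 20 mg/mL (6.1.4). Planned cycles 17 (6.1.9).

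**Reproducing the stated volume.** Volume = dose / concentration. At 50 mg/mL, 350 / 50 = 7 mL, so the protocol's figure is exactly right for that strength.

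**The other strength.** At 25 mg/mL, 350 / 25 = 14 mL. The stated 7 mL gives 7 x 25 = 175 mg, and 175 / 350 = 50% of the dose.

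| Vial strength | Amount in 7 mL | Share of 350 mg | Volume needed for 350 mg |
|---|---|---|---|
| 50 mg/mL | 350 mg | 100% | 7 mL |
| 25 mg/mL | 175 mg | 50% | 14 mL |

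**Would the dilution limit reveal it?** Final volume = amount / final concentration.

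- 350 mg is within 1 to 20 mg/mL at volumes from 350 / 20 = 17.5 mL to 350 / 1 = 350 mL.
- 175 mg is within it at volumes from 175 / 20 = 8.75 mL to 175 / 1 = 175 mL.
- The two ranges overlap from 17.5 to 175 mL, and there the limit is met with either amount.

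The final volume is not stated, so two illustrations: at 100 mL the concentrations are 3.5 and 1.75 mg/mL, both in range; at 250 mL they are 1.4 and 0.7 mg/mL, and the half dose falls below the lower limit. The half dose drops below 1 mg/mL only above 175 mL.

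**Upper bound for one patient.** If every infusion over 17 cycles were affected, the total would be 17 x 175 = 2,975 mg instead of 17 x 350 = 5,950 mg.

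**Uveitis, side by side.** In the Grade 2 row of Appendix 1, the line on approval before resumption agrees with section 6.1.8, which allows a restart after grade 2 uveitis if it resolves to grade 1 or below and the site PI approves. The same line appears in the Grade 3-4 row, where section 6.1.8 allows no restart.

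**The case against.** The strongest reply is that no number is miscalculated: 7 mL is correct for 50 mg/mL, and the document does not say that 25 mg/mL vials will actually be shipped. The binding requirement is stated in milligrams, and section 6.1.5 gives preparation to a pharmacist or other qualified individual. Diluting to a target concentration also requires knowing how many milligrams were drawn. A preparer who works that out from the label would see 175 mg against an order for 350 mg. Dosing records (6.1.10), accountability (6.2) and reconciliation (6.1.1) add further checks, and the pharmacy manual may give volumes by strength.

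Most of this bears on how likely harm is, and it stands to that extent. The documents also give no exposure-response data, so no effect on the response rate can be quantified. The sample size calculation in section 10.5 is untouched.

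None of it makes sections 6.1.2 and 6.1.4 compatible. Records and reconciliation come after the dose has been prepared. The pharmacy manual was not available for this review and is not cited for volumes; if it does give them by strength, section 6.1.4 contradicts it at 25 mg/mL. If only 50 mg/mL is shipped, it is section 6.1.2 that needs the edit.

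On uveitis, the dosing column of the Grade 3-4 row says to discontinue, and Appendix 1 describes itself as guidance and refers back to the dose-adjustment section. The stray line is therefore low risk, though still inconsistent.

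**Conclusion.** The concern holds. As written, section 6.1.4 produces the wrong dose for one of the two vial strengths the protocol permits, and no other section corrects it.

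The size per affected infusion is certain: 175 mg instead of 350 mg. How many patients would be affected cannot be determined from the documents. The range is 0 to 27, with 0 if only 50 mg/mL vials are supplied. Any actual under-dosing assumes that 25 mg/mL vials are dispensed, that the 7 mL is taken literally, and that nobody catches it; the 17-cycle total above further assumes that this happens at every infusion.

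This should be fixed because it is a drug-preparation instruction and the correction is simple, not because an effect on the trial result has been shown. The uveitis inconsistency is real but minor.

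**What to change.** In section 6.1.4, tie the volume to the strength: 7 mL at 50 mg/mL and 14 mL at 25 mg/mL, or simply the volume containing 350 mg. Alternatively, remove 25 mg/mL from section 6.1.2 if that strength will not be supplied.

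If 25 mg/mL stays, also revisit the wording that has the dose drawn from a single vial. Fill volume is not stated, and a vial holding less than 14 mL would mean using more than one.

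In the same amendment, delete the resumption line from the Grade 3-4 uveitis row of Appendix 1. If the clinical team does want to allow a restart, change section 6.1.8 instead.

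The cost is protocol wording only, plus a check that the pharmacy manual says the same.
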